We propose a prospective, double-blinded, randomized trial. According to our patient population and incidence of morbid obesity, enrollment would likely occur over a 2 to 3-year period. We have a delivery rate of 3500 per year. Previous data from our institution show that at least 11% of our patients are morbidly obese. We will therefore expect 800-900 morbidly obese women to deliver at our institution per year. We anticipate to complete enrollment before the protocol's third annual renewal.

Subject identification and recruitment:

Women admitted to the Duke Birthing Center for spontaneous or induced vaginal delivery will be screened. After usual consultation with the anesthesia team is completed and consent for anesthesia services are obtained, eligible patients will be approached to by a member of the study team. As indicated below, we will plan to enroll 130 patients (65 for the DPE group and 65 for the EPL group) and consent 150 women to reach this goal.

Inclusion criteria for study eligibility include: ages 18-45, singleton, vertex fetuses at 37-41 weeks' gestation, nulliparous and multiparous women, cervical dilation of 2-7cm, BMI ≥ 35 kg/m², pain score > 4, and English-speaking ability. Women with diseases of pregnancy that increase the risk of assisted vaginal delivery or cesarean delivery (i.e. major cardiac disease, chronic pain, chronic opioid use, prior cesarean delivery, and maternal pelvic/hip disease) are will be excluded from the study. Women who cannot speak English will be excluded. *Subject competency:* Only competent subjects will be approached to participate in this study. *Costs to the subject:*

There will be no additional cost to the subjects as a result of participation in this research study. There will be no compensation to patients for their participation in this study.

Epidural technique:

Once the patient requests a labor epidural, the usual standard of care for epidural placement will be initiated. The patient will have at least one 18g intravenous catheter and will receive 500-1000mL fluid administration. Vitals will be monitored by the labor nurse, including continuous pulse oximetry, non-invasive blood-pressure monitoring, and external tocodynamometry. Anesthesia time-out will be performed by the anesthesia provider with participation from the nurse and the patient.

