All patients will receive a neuraxial technique in the sitting position at L3/4 or L4/5 using loss of resistance to saline. In the DPE group, a 25-g Whitacre needle will be used to puncture the dura. In both groups, the epidural catheter will be threaded 5 cm in the epidural space with an initiation dose of 15 ml of ropivacaine 0.1% with fentanyl (2 mcg/ml) over 6 minutes as per standard practice. Labor analgesia will be maintained by programmed intermittent bolus with 6 ml of the same solution every 45 minutes starting 30 minutes after the initial dose. Patients will have patient-controlled epidural analgesia (PCEA) available with an 8 ml dose per demand, every 10 minutes, for a maximum dose of 45 ml for every hour.

Assignment of Study Cohorts:

Study participants will be randomized by computer-generated sequence to EPL or DPE arms, stratified by class of obesity (BMI \geq 35<40 kg/m², \geq 40<50 kg/m² and \geq 50 kg/m²) and by parity (nulliparous versus multiparous). Patients will be assigned to one of the four study arms by computer-generated, randomized sequence in order to balance baseline characteristics across the arms. This will be a double-blinded study. After the consented and enrolled participant

requests labor epidural, a study member will give the anesthesia provider a sealed envelope with study assignment for either standard EPL or DPE technique.

Protocol for Breakthrough Pain

- If the patient has uneven or unilateral level, the provider will withdrawal catheter 1cm from skin and bolus 5ml of epidural mix. As fetal heart rate allows for maternal repositioning, the patient will lay lateral position with unblocked side in the dependent position. (up to 3 catheter adjustments)
- If the patient has bilateral levels at that below T10 to ice, the patient will be administered 5 ml off epidural pump, up to 3 times in 15 minutes.
- If the patient has pain despite T10 levels, the provider will administer Fentanyl 100 mcg via epidural.
- If analgesia continues despite these interventions up to 3 times within 60 minutes, the attending anesthesiologist will determine if epidural catheter needs replacement.

Data analysis and monitoring:

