Further analysis of the difference in the composite outcome between the two epidural techniques will be conducted via multivariate logistic regression to account for potential confounders. Comparison of additional secondary outcomes between the epidural techniques of

maternal adverse events, total labor epidural time, total anesthetic dose required, mode of delivery, and degree of motor block will be compared with χ^2 tests and logistic regression. The time to numeric pain rating scale ≤ 1 will be compared between the two epidural techniques via Kaplan-Meier estimates and log-rank tests.

Data will be monitored closely for the occurrence of adverse events (AE) and reported to the IRB as needed. If unanticipated AEs or if expected events appear to be occurring more frequently than expected, those AEs will be explored per treatment arm.

In accordance with federal regulations, the PI will monitor for, review, and promptly report to the IRB, appropriate institutional officials, sponsor, coordinating center and the appropriate regulatory agency head all unanticipated problems involving risks to subjects or others that occur in the course of a subject's participation in a research study (45 CFR 46.103(b)(5)(i) and 21 CFR 56.108(b)(1)), all AE reports will be reported per the DUHS IRB policies.

Data storage and confidentiality:

Study records will remain confidential as required by law. Federal Privacy regulations ensure privacy, security and authorized access. Patient identifiers including but not limited to name, social security number, address, and telephone number will not be disclosed outside of the Duke University Health System (DUHS). For records shared with parties outside of DUHS, patients will receive a unique code number. The key to the code will be kept in a locked file in [name] office.

Risk/benefit assessment:

The will be no benefit to subjects from participating in the study, since standard of care regimens will be used in this study. The information gained from the study will help elucidate if

DPE offers benefits over standard EPL for initiation and maintenance of labor analysis in our practice. Risks of epidural analysis are the same irrespective of participation in the study. These are 1.5% rate of unintentional dural puncture with epidural needle, <1% risk of post-dural pucture headache, inadequate analysis, and unintentional intravascular or subarachnoid injection. ^{19,20}

References:

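### Total epidural time and total dose have no prespecified covariate and no method suited to continuous data; entry cervical dilation is a cheap, useful covariate that the plan leaves unnamed

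*Combined protocol and SAP*

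**What the plan says.** Subject identification and recruitment lists "cervical dilation of 2-7cm" among the inclusion criteria, so dilation is assessed before a woman can be randomized. Under Assignment of Study Cohorts, randomization is "stratified by class of obesity" (three BMI classes) and "by parity (nulliparous versus multiparous"); dilation is not a factor.

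Data analysis and monitoring lists total labor epidural time and total anesthetic dose as secondary outcomes. Statistical Methods then groups them with categorical outcomes: "total labor epidural time, total anesthetic dose required, mode of delivery, and degree of motor block will be compared with" chi-square "tests and logistic regression". It names no covariates, cut-points or categories for them.

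Adjustment is mentioned once, for the composite primary outcome, whose further analysis "will be conducted via multivariate logistic regression to account for potential confounders". Those confounders are not listed.

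Under Epidural technique, programmed boluses of 6 ml are given every 45 minutes, with patient-controlled doses in addition, so total dose accumulates with time.

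**The concern.** A woman whose epidural is placed at 2 cm will usually have more labor ahead of her than one placed at 7 cm. If so, part of the spread in epidural time, and in the dose that accrues with it, reflects stage of labor at entry and not technique. Left out of the model, that spread stays in the error term. If one arm happens to be placed earlier in labor, it will tend to show longer times and larger doses, and the plan fixes no way to correct for this.

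The named methods add to the problem. Chi-square and logistic regression need categories, so time and dose would have to be cut at points that are not yet chosen. The covariates of the logistic models are equally open. Both choices could then be made after the data are seen.

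**Working it through.** **The plan's own figure.** With 35% versus 14%, two-sided alpha 0.05 and 80% power, the mean rate is 0.245:

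n = [1.96 × √(2 × 0.245 × 0.755) + 0.8416 × √(0.35 × 0.65 + 0.14 × 0.86)]² / 0.21² = (1.192 + 0.496)² / 0.0441 ≈ 65 per arm, with power 80.2% at 65.

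The figure reproduces. It concerns the composite only; no size or power is stated for time or dose.

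**Dose and time.** 6 ml per 45 minutes is 6 × 60/45 = 8 ml per extra hour from programmed boluses, before patient-controlled doses.

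**Gain by correlation.** Let r be the correlation between dilation and the outcome (assumed; not in the documents). Adjustment multiplies the standard error by √(1 − r²), and the equivalent sample size is 130/(1 − r²). Unadjusted, the difference detectable with 80% power is (1.96 + 0.8416) × √(2/65) = 0.491 SD.

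| r | SE reduction | Detectable difference | Equivalent N |
|---|---|---|---|
| 0.2 | 2.0% | 0.482 SD | 135 |
| 0.3 | 4.6% | 0.469 SD | 143 |
| 0.5 | 13.4% | 0.426 SD | 173 |

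**Gain under assumed durations.** All of these inputs are assumptions:
- dilation uniform over whole centimetres from 2 to 7;
- mean remaining time in nulliparous women falling linearly from 10 to 6 h, 12 to 5 h or 12 to 4 h over that range;
- multiparous women at 0.6 of this, with parity split equally;
- gamma scatter with CV 0.6 in every scenario.

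Residual variances of log time come from 400,000 simulated women per scenario. Power for a 1.3-fold difference is Φ(ln 1.3 / √(2σ²/65) − 1.96).

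| Scenario | Variance removed beyond parity | Power, unadjusted | Power, parity | Power, parity + dilation |
|---|---|---|---|---|
| 10 to 6 h | 7% | 54% | 59% | 62% |
| 12 to 5 h | 17% | 50% | 54% | 62% |
| 12 to 4 h | 24% | 47% | 51% | 62% |

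For example, in the first scenario the SD of log time is about 0.727. The unadjusted SE is 0.727 × √(2/65) = 0.1275, and 0.2624/0.1275 − 1.96 = 0.10, which gives 54%. Parity plus dilation leaves 0.819 of the variance, so the SE is 0.1154, and 0.2624/0.1154 − 1.96 = 0.31, which gives 62%. A model with arm and dilation but without parity reaches only about 56% in each scenario, so the stratification factors belong in the model.

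**Chance imbalance.** Whole-centimetre values 2 to 7 have SD √(35/12) = 1.71 cm. The between-arm difference in mean dilation has SD 1.71 × √(2/65) = 0.30 cm. The fitted slopes are about −0.10, −0.17 and −0.22 per cm on the log scale. A 2-SD imbalance (0.60 cm) therefore shifts time by exp(0.10 × 0.60) − 1 ≈ 6% up to exp(0.22 × 0.60) − 1 ≈ 14%. If dilation is treated as continuous, its SD is 5/√12 = 1.44 cm and the SD of the arm difference is 0.25 cm, so the shifts are somewhat smaller.

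**Cost of categorizing.** A median split of a normally distributed outcome has efficiency 2/π = 0.64, as if about 130 × 0.64 = 83 women were analyzed. Omitting dilation costs as much only when 1 − r² = 0.64, that is, at r = 0.6.

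**The case against.** The strongest reply is that the plan does not forbid adjustment. Logistic regression is named beside the chi-square test, and its covariates are simply left open. A reader might infer that time and dose will be analyzed without any covariate; the text supports only that none is prespecified and that dilation is not named. The composite model's unlisted confounders could also include dilation.

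A reader might also infer that the comparison is biased. It is not: randomization makes the unadjusted comparison valid on average, its standard error already allows for chance imbalance, and parity, which probably relates to labor length, is balanced by stratification.

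Nor do the figures show a chance shift as large as an effect of interest. The 6-14% needs an imbalance seen in roughly one trial in 20, and on the log scale even 14% (ln 1.14 = 0.131) is half of a 1.3-fold effect (ln 1.3 = 0.262).

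Finally, the documents give no labor durations. The Background cites a series in which 48% of morbidly obese women needed emergency cesarean, and such endings could weaken the link between dilation and epidural time.

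All of this stands, and it limits the size of the point. It does not answer the two gaps: the stated methods do not suit continuous outcomes, and the covariates are not fixed in advance.

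**Conclusion.** The point holds as a modest, inexpensive improvement to the analysis of two secondary outcomes. The plan names methods that do not fit continuous time and dose, and it fixes no baseline covariate, although a plausible predictor is assessed for eligibility in every woman. What may be lost is efficiency and accuracy given the imbalance that occurs; the design is not biased.

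The size depends on inputs outside the documents: a 2-5% lower standard error at r 0.2-0.3, and about 13% at r 0.5. Under the assumed durations with CV 0.6, adding dilation to parity raises power for a 1.3-fold difference in epidural time by about 3, 8 or 11 points, to about 62%. These gains are measured against a log-scale continuous analysis, which the plan does not contain; if the outcomes were dichotomized as the named tests require, that loss would probably be the larger one. The power figures are for epidural time. Dose was not modelled separately, because patient-controlled use is unknown. No gain is claimed for the composite, and the sample size of 130 is unaffected.

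**What to change.** In Statistical Methods, take total labor epidural time and total anesthetic dose out of the sentence on chi-square tests and logistic regression. Compare each by linear regression on a suitable scale (for example log) on arm, with these covariates:
- cervical dilation recorded before randomization, in cm, as a linear term;
- parity;
- BMI class, as used in the stratification.

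Fix the scale and covariates before unblinding. Do not adjust dose for epidural time, which arises after randomization and may itself be affected by technique; dose per hour can be shown as a separate supportive measure.

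The cost is SAP wording, one degree of freedom for dilation beyond the stratification factors, and making sure that the pre-randomization dilation value is kept in the study data, since the documents give it only as an eligibility criterion. Enrollment, treatment and the primary chi-square test do not change.

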The primary outcome of this study is block quality which will be defined by a composite of five components (1) asymmetric block after 30 minutes of initiation, (2) top-up interventions, (3) catheter adjustments (4) failed catheter requiring replacement, and (5) failed epidural requiring general anesthesia or replacement neuraxial anesthesia for emergency cesarean section. The composite outcome is a practical endpoint for our study because while necessary to determine block quality, incidence of failed epidural or one-sided epidurals are rare. All five components are of similar importance when assessing the quality of epidural analgesia. Therefore, this outcome definition will increase the power of the study, without sacrificing clinical relevance or feasibility.

Block level will be measured by temperature discrimination with ice, and levels that are greater than two dermatomal levels would be considered asymmetric. Lower extremity dermatomal levels will be assessed by stimulating the inguinal crease (L1), anterior thigh (L2), medial knee (L3), medial malleolus (L4), between the great and second toe (L5), the lateral heel (S1), and the medial popliteal fossa (S2). On the thoracic levels, the torso will be assessed bilaterally at the mid-clavicular line.

Secondary outcomes include time to numeric pain rating scale ≤1, maternal adverse events (hypotension, fetal bradycardia, PDPH), motor block, duration of second stage of labor, total labor epidural time, total anesthetic dose required, PCEA use, and mode of delivery.

Statistical Methods:

The primary assessment of difference in the composite outcome between the two epidural techniques will be conducted via chi-square test. Using data from a recent retrospective study on labor maintenance regimens published by our group, we expect the composite event rate to be 35% in the group receiving EPL.¹⁷ Based on the findings by Hess *et al.* of a 62% relative reduction in breakthrough pain with a CSE technique compared to an EPL, we will define a clinically meaningful effect in our study as a similar reduction in the composite outcome to be 14% in the DPE group, which corresponds to an odds ratio of $0.30.^{18}$ A two-sided χ^2 test for the difference in composite outcome rates between epidural techniques at alpha level 0.05 will reach 80% power to detect an odds ratio of 0.30 comparing DPE to EPL in a study of 130 patients (65 DPE and 65 EPL).

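### Time to pain score ≤1 is tested with an unadjusted log-rank; adjusting for pain before the block would cost little and probably gain some power on this secondary outcome

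*Combined protocol and SAP*

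**What the plan says.** - **Outcome.** Under Data analysis and monitoring: "Secondary outcomes include time to numeric pain rating scale ≤1". It is one of several secondary outcomes and the only one listed that measures onset.
- **Analysis.** Under Statistical Methods: "The time to numeric pain rating scale ≤ 1 will be compared between the two epidural techniques via Kaplan-Meier estimates and log-rank tests". That is the whole plan for this outcome.
- **Entry.** The inclusion criteria under Subject identification and recruitment require "cervical dilation of 2-7cm, BMI ≥ 35 kg/m², pain score > 4". The scale, and the time at which the score is taken, are not given.
- **Randomisation.** Under Assignment of Study Cohorts, allocation is "stratified by class of obesity" "and by parity (nulliparous versus multiparous". Entry pain is not a factor.
- **Adjustment elsewhere.** Further analysis of the composite "will be conducted via multivariate logistic regression to account for potential confounders". A list of other secondary outcomes, ending "mode of delivery, and degree of motor block will be compared with", is assigned chi-square tests and logistic regression. Time to pain score ≤1 is not in that list.

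**The concern.** The event is a fixed absolute level, but women start at different heights above it. On a 0-10 integer scale (assumed), a woman entering at 5 must fall 4 points and a woman entering at 10 must fall 9. Entry pain is therefore likely to predict how long the event takes. A log-rank that ignores a prognostic baseline value loses power as that value becomes more strongly prognostic. Any chance difference in entry pain between the arms also stays in the treatment comparison, because neither the randomisation nor the analysis deals with it. At stake is the precision of the trial's only measure of speed of relief, which the Background lists among the benefits of the dural puncture technique.

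**Working it through.** **1. The plan's own figure.** From Statistical Methods: composite 35% v 14%, two-sided alpha 0.05, 80% power, 65 per arm. With mean rate 0.245:

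n = [1.960 × √(2 × 0.245 × 0.755) + 0.842 × √(0.35 × 0.65 + 0.14 × 0.86)]² / 0.21² = (1.192 + 0.497)² / 0.0441 = 64.7, so 65 per arm. Power at 65 is 80.2%. The figure reproduces. It concerns the composite only; the plan gives no hazard ratio, event count or power for onset.

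**2. What 130 women can detect on onset.** If all 130 reach the event, Schoenfeld's formula gives a hazard ratio of exp[(1.960 + 0.842) / √(130/4)] = exp(2.802 / 5.701) = 1.63 at 80% power. This is why about 1.65 is used below. It is an assumption, not a figure from the plan.

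**3. Power, unadjusted log-rank v Cox adjusted for entry pain.** Both simulations have 65 per arm, entry scores 5 to 10 with mean about 7.8, and censoring at 60 minutes. All of these except the arm size are assumptions, as are the time distributions.

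Simulation A: hazard ratio 1.65, Weibull times (shape 1.5, median 18 minutes) read every 2 minutes, 1,500 trials per cell.

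| Log-hazard per entry point | Log-rank | Adjusted Cox | Gain (points) |
|---|---|---|---|
| 0 | 76.9% | 75.7% | -1 |
| -0.15 | 71.9% | 74.1% | 2 |
| -0.30 | 63.7% | 76.1% | 12 |
| -0.45 | 56.1% | 74.3% | 18 |

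Simulation B: hazard ratio 1.64, exponential times (control median 15 minutes), 3,000 trials per cell. The stratified log-rank uses entry pain below 8 v 8 or more.

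| Hazard multiplier per point (log) | Log-rank | Stratified log-rank | Adjusted Cox |
|---|---|---|---|
| 1.0 (0) | 77.7% | 76.5% | 77.1% |
| 0.9 (-0.11) | 76.3% | 76.6% | 77.8% |
| 0.8 (-0.22) | 71.4% | 74.3% | 77.4% |
| 0.7 (-0.36) | 59.8% | 69.8% | 76.2% |
| 0.6 (-0.51) | 51.5% | 65.4% | 74.9% |

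The Monte Carlo standard error of one cell in A is about √(0.72 × 0.28 / 1,500) = 1.2 points, so the smallest gaps are not sharply estimated.

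**4. A larger effect.** With the model of A, continuous times and hazard ratio 2.0 (4,000 trials per cell), power is 96% v 97% at -0.15, 93% v 97% at -0.30 and 88% v 97% at -0.45. At hazard ratio 2.5 the largest gap is 2 points.

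**5. Which prognostic strengths are plausible.** When the effect is derived from a model in which pain falls exponentially or linearly from the entry score, with log-normal between-woman speed (SD 0.4 to 0.8), the implied log-hazard per point is -0.11 to -0.31 and the gain about 1 to 8 points. A value of -0.45 would give a woman entering at 10 a hazard of exp(-0.45 × 5) = 0.11 times that of a woman entering at 5. That is an extreme case.

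**6. Type I error.** Averaged over randomisation, the unadjusted log-rank rejects in 3.5% to 5.0% (A) and 4.7% to 5.4% (B) of null trials. The adjusted Cox rejects in 3.7% to 4.8% (A) and 4.9% to 6.0% (B).

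**7. Chance imbalance.** With an entry-score SD of 1.35 (A) or 1.58 (B), the difference in arm means has standard error 1.35 × √(2/65) = 0.24 or 1.58 × √(2/65) = 0.28 points. In A, a 2-SE imbalance at -0.30 per point shifts the hazard ratio by exp(0.30 × 0.48) = 1.15-fold. In B, a 0.56-point imbalance shifts it by 0.8^0.56 = 0.88 or 0.7^0.56 = 0.82. Given that imbalance, the unadjusted test rejects a true null 9% or 12% of the time, and the adjusted test 5% to 6%.

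**The case against.** **Secondary outcome.** The sample size was set for the composite, the hypothesis concerns block quality, and the Background puts figures only on benefits that relate to the composite. No power on onset was promised. This stands: a reader might infer that the trial falls short of a planned power for onset, but the documents plan none.

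**Valid test.** A reader might infer that the log-rank is invalid or inflates false positives. It does not. Chance imbalance is already covered by the unconditional error rate, and a 2-SE imbalance arises in only about 5% of trials. What remains is lost efficiency and a comparison that is off in the trials where imbalance occurs.

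**Unknown prognostic strength.** Both arms receive the same initiation dose, and the documents give no data linking entry score to onset time. A larger fall need not take proportionately longer. This stands as a limit on size. It does not remove the point, because adjustment costs about a point of power or less if entry pain proves irrelevant.

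**Recording of the score.** The documents give only a cutoff. Women are screened on admission and the technique is assigned after an epidural is requested, so the eligibility score may predate the block. If it tracks pre-block pain with added error of SD 1.5 (assumed), the gain at hazard ratio 1.65 and -0.30 falls from 10 points to 4; with SD 2.5 it is about 1. This stands, and it is why the fix asks for the last score before placement. It also means the documents do not support saying that no new data are needed.

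**Model tested.** The simulations adjust for entry pain alone and, apart from the check in step 5, generate the data from the same proportional-hazards model. The contributions of BMI class, parity and cervical dilation were not quantified.

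**Conclusion.** The point holds as a modest, inexpensive improvement to a secondary analysis. Under -0.15 to -0.30 log-hazard per entry point, adjustment gains about 2 to 12 points of power at hazard ratio 1.65 and about 1 to 4 points at 2.0. It gains nothing if entry pain is not prognostic. These figures rest on assumed effect sizes, an assumed 0-10 scale and entry-score distribution, assumed time distributions, and a baseline score that reflects pain just before the block.

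The 18-point gain at -0.45 should not be read as the expected loss, since it needs the extreme strength noted above. Nor does anything here show that cervical dilation must be in the model; entry pain carries the case. The primary comparison and the sample size of 130 are unaffected.

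**What to change.** Keep the Kaplan-Meier curves as the display. Pre-specify, as the test for this outcome, a Cox model with technique, pain score (linear), BMI class and parity. The pain score should be the last one taken before epidural placement, or the eligibility score if that is the one kept. Cervical dilation is optional. A log-rank stratified by entry-pain band is an acceptable alternative, but it recovers only part of the gain (69.8% against 76.2% for Cox and 59.8% unadjusted, at a multiplier of 0.7). The choice belongs in the plan now, because adjusting only after an imbalance is seen would be data-driven.

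The cost is a sentence or two under Statistical Methods and confirmation that the numeric score and its time are recorded. If they are not, one field must be added to data collection. The other downsides are a proportional-hazards assumption and a hazard ratio that is conditional on the covariates. No additional patients are needed.
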